## BP Relapse

In the event of a suspected BP relapse (see [Table 6](#) for definition), the participant should attend an unscheduled visit. A BPDAI evaluation will be conducted at the time of the relapse, or as soon as possible afterwards.

Investigators will be required to record details pertaining to each relapse event in the eCRF from baseline (Visit 2) until IPD visit/end of treatment and follow-up visit. Details should include the BPDAI activity and pruritus score and the required intervention(s), eg, OCS dose increase, the OCS dose at the time of relapse, addition of immunosuppressive therapy or requirement for hospitalization. Participants who require the addition of OCS after taper or an increase in the dose of OCS will be defined as having a relapse.

The management of participants who relapse will be according to standard of care. See [Section 6.5.1](#) for further details. The participant's relapse is managed with the addition of OCS and tapering should be recommended as soon as the relapse has been appropriately controlled as per current guidelines ([Feliciani et al 2015](#)). In case of a relapse during steroid tapering, the OCS dose may be increased to the previous dosage that symptoms were controlled. For recurrent relapses the OCS dosing regimen and tapering schedule will be at the Investigator's discretion. If the participant requires therapy other than OCS (eg, immunosuppressants), the study treatment may need to be discontinued but this should be discussed with the study physician prior to decision making. In the event that discontinuation of IP is required, the participant will still be asked to continue with the study assessments until the end of the double-blind period at Week 36. For relapse during OLE, the use of topical and/or oral corticosteroids and the schedule of taper will be at the discretion of the Investigator; however, it is recommended to follow the protocol taper schedule. The goal of therapy will be to taper off steroids to benralizumab monotherapy as soon as clinically indicated. In the event that the Investigator will need to control relapse with an immunosuppressant in the OLE, the participant will be withdrawn from the study and will not receive further benralizumab therapy. Participants may additionally be asked to allow future contact to provide follow-up clinical details regarding their health and information on disease state.

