### 8.1.1.2 Bullous Pemphigoid Disease Area Index

Bullous Pemphigoid Disease Area Index is a clinician completed tool that is used for independent disease severity assessment to measure disease extent in BP ([Wijayanti et al 2017](#)).

The Investigator will be required to complete the BPDAI on a tablet at screening (Visit 1), randomization (Visit 2), and then at each visit until the end of the double-blind treatment period, at the time of presentation with relapse or suspected relapse, at unscheduled visit, and at IPD/end of treatment and follow-up visit.

During the subsequent OLE (if applicable), the Investigator is required to complete BPDAI Q4W, at unscheduled visits (eg, in the event of a relapse), and at the IPD/end of treatment and follow-up visit.

The BPDAI tool computes 2 scores: total BPDAI activity and total BPDAI damage. The total BPDAI activity score (0 to 360) is the arithmetic sum of the 3 subcomponents – cutaneous blisters/ erosions, cutaneous urticaria/erythema, and mucosal blisters/ erosions. The total BPDAI damage score (0 to 12) is the arithmetic sum of the items rated regionally for damage caused by more permanent features such as post-inflammatory hyperpigmentation, scarring and other. BPDAI quantifies lesion number and size thresholds. Lesions are rated based on the regions affected. BPDAI gives additional weighting to areas of the skin primarily affected in BP, such as the limbs, and less emphasis to scalp and face. The BPDAI total activity and BPDAI damage give an indication of disease activity, with higher scores indicating greater disease activity or damage.

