### **8.1.2 Patient-reported Outcomes**

Participants will complete all PRO assessments using provisioned devices. All participants will complete PROs on the tablet at onsite visits. Daily PROs are completed on the handheld device at home. If the Investigator believes that the participant has a medical condition (eg, BP skin lesions on the fingers/hand, neurologic condition affecting the fingers/hand, or severe visual impairment), then an exemption from at-home PROs may be requested from the AstraZeneca study physician prior to the screening visit.

The Investigator will ensure that participants are properly trained on the use of the handheld PRO device and the importance of completing at-home assessments as scheduled. Compliance should be checked weekly (at a minimum) to ensure that the participant is completing the assessments as scheduled, including a check of the daily oral steroid doses taken. The Investigator or designee will be responsible for monitoring participant adherence with the daily assessments and follow up as necessary.

The at-home handheld device will be programmed at Visit 2 with reminder alarms for the daily questionnaires. Study site staff will be able to adjust alarms for specific participant needs as needed. The participant will be required to complete a training module before taking the device home.

Participants must bring the at-home handheld device to every visit.

Confirmation of the visit in the PRO system, completion of at-site PRO assessments, and review of participant compliance with at-home PRO assessments should be completed prior to other study procedures. The timing and frequency for each PRO is provided in [Table 3](#). The handheld device will be returned to the study site at Visit 22 (Week 72) or at the IPD visit for participants who prematurely discontinue from IP and are unwilling/unable to continue with visit procedures.

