### **Change from baseline in BPDAI activity score at Week 36**

BPDAI activity score is a continuous endpoint that will be completed at the visits specified in the SoA ([Table 2](#)) during the initial 36-week treatment period.

The estimand strategy is outlined in [Table 10](#) above. For this endpoint, intercurrent events of rescue use with OCS after having previously achieved disease control and restricted medication use are considered unfavorable outcomes and will be handled with a composite strategy whereby participants experiencing these events prior to Week 36 will have their last observation prior to rescue/restricted medication use carried forward to Week 36. For participants who discontinue the study without having rescue or restricted medications, missing data at Week 36 will be imputed using multiple imputation based on participants who don't have rescue/restricted medication use. Once these imputations are made, the available change from baseline in BPDAI score at Week 36 will then be analyzed using an analysis of covariance (ANCOVA) model.

The model will include change from baseline at Week 36 as the dependent variable, baseline BPDAI score as a continuous covariate, and treatment, baseline disease severity, and time of

BP diagnosis as categorical covariates. The model will be used to estimate the mean change from baseline at Week 36 for each treatment group and the difference versus placebo, with corresponding 95% confidence limits. A p-value, corresponding to a 2-sided test, will be presented to compare the benralizumab and placebo treatment groups.

To support this analysis, observed means and mean changes from baseline will be summarized using descriptive statistics by treatment group and each scheduled visit up to Week 36. In addition, the cumulative distribution function of absolute changes from baseline in BPDAI activity score at Week 36 will also be plotted, to allow the treatment difference at various response thresholds to be explored. Responder analyses using minimal clinically important differences presented in the literature ([Wijayanti et al 2017](#)) may be presented, if appropriate.

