3 PRIMARY AND SECONDARY VARIABLES

3.1 General definitions

3.1.1 Baseline definition

For efficacy, the last recorded value on or prior to the date of randomization will serve as the baseline measurement. If time is collected and relevant for the analysis, the assessment performed the same day but at a time prior to randomization will be included in the baseline definition.

For safety and PK, the last recorded value on or prior to the first dose of study treatment will serve as the baseline measurement. If time is collected, the assessment performed the same day but at a time prior to the first dose of study treatment will be included in the baseline definition.

When time of assessment is not recorded or missing, it is assumed that assessments recorded on the date of randomization (or the date of the first dose of study treatment, depending on the endpoint) were performed prior to randomization (or dosing), except in cases of protocol specified post-dose assessments. If there is no value prior to randomization (or dosing), then the baseline value will not be imputed and will be set to missing.

No data known to be collected post first dose will be used in determining the baseline value, unless otherwise specified.

For physical examinations baseline data will be collected at Visit 2 before first dose of IP.

For the Peak Pruritus Numeric Rating Scale (NRS), which is calculated as the average of daily scores over 7 days, change will be assessed by comparison to the assessments on the date

when disease control was recorded and on the 6 days after. Further details on scoring for PROs will be provided in Section [3.6.1](#).

Additional analyses for the participants who switch from placebo to benralizumab at Week 36 may be performed where the baseline value is set to the last recorded value prior to starting benralizumab (ie, likely the Week 36 measurement) to obtain an assessment of the changes occurring while receiving benralizumab.

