Total Mucosa		/120											

Any participant with missing data at a specific time point will be considered as having a missing score at that time point.

The set of intercurrent events for this estimand consists of participants who use restricted medications, participants who have their OCS dose increased as rescue therapy after having previously achieved disease control and participants who withdraw from the study.

Participants who receive medications deemed to be intercurrent events as per Section [3.1.5.2](#) will have their last BPDAI activity score observed prior to the date of start of restricted medication carried forward to Week 36. If baseline is the last available assessment prior to the date of start of restricted medication, then it will be used to impute the missing data.

Likewise, participants who need to increase their OCS dose as a rescue therapy to treat their BP after having previously achieved disease control will have their last BPDAI activity score observed prior to the date of OCS dose increase recorded with start date > date of disease control assessment carried forward to Week 36. If baseline is the last available assessment prior to the date of OCS dose increase, then it will be used to impute the missing data.

For restricted medications/OCS during the study missing/partial start dates are not allowed. For participants who withdraw from the study without having rescue or restricted medications, missing BPDAI activity score at Week 36 will be imputed using multiple imputation based on participants who don't have rescue/restricted medication use. The same approach will be applied to those participants with missing data at Week 36 for any other reason. Further details are provided in Section [4.2.7.3](#). For the summary statistics, missing values will remain missing.

3.3.4 Change from baseline in BPDAI-Pruritus score at Week 36

The BPDAI-Pruritus is a continuous endpoint that will be completed at the visits specified in the CSP Table 2.

The BPDAI-Pruritus is a separate component of the BPDAI that asks the participant to grade the severity of pruritus over the past 24 hours, the past week, and the past month. For each recall period, severity of pruritus is rated on an NRS ranging from 0 for no itch to 10 for maximal itching.

The BPDAI-Pruritus score will be computed as the sum of the three components ranging from 0 to 30.

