The change from baseline in the BPDAI-Pruritus score at Week 36 will be analysed as a key secondary endpoint.

Any participant with missing data at a specific time point will be considered as having missing severity of pruritus at that time point.

The set of intercurrent events, the estimand approach and the imputation rules are the same as described in Section 3.3.3 for the change from baseline in BPDAI activity score at Week 36.

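### The LOCF cut-off for the two BPDAI key secondary endpoints excludes a relapse score dated on the day OCS is increased or restricted medication starts

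*SAP*

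**What the plan says.** SAP 3.3.3 handles two events in the BPDAI activity analysis by last observation carried forward (LOCF). For OCS rescue after disease control, participants "will have their last BPDAI activity score observed prior to the date of OCS dose increase" carried to Week 36. For restricted medication, the value used is the "last BPDAI activity score observed prior to the date of start of restricted medication carried forward to Week 36". Each sentence has a follow-up that falls back on baseline when no later score qualifies. SAP 3.3.4 adopts the same handling for BPDAI-Pruritus: "the imputation rules are the same as described in Section 3.3.3". SAP 4.2.7.3 points back to 3.3.3 and sets no other cut-off.

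Protocol 9.4.2.2 ties the rule to the use of the medication, not to its calendar date: participants with these events "will have their last observation prior to rescue/restricted medication use carried forward to Week 36". It classes both events as unfavourable and handles them with a composite strategy.

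On the timing of scores, protocol 8.1.1.2 requires the BPDAI "at the time of presentation with relapse or suspected relapse, at unscheduled visit", among other occasions. The relapse record in protocol 8.1.1.1 links the scores to treatment: "Details should include the BPDAI activity and pruritus score and the required intervention(s), eg, OCS dose increase". For patient-reported outcomes, protocol 8.1.2 sets an order within the visit: "completion of at-site PRO assessments, and review of participant compliance with at-home PRO assessments should be completed prior to other study procedures".

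Elsewhere the SAP writes inclusive cut-offs. In 3.1.1, for efficacy, "the last recorded value on or prior to the date of randomization will serve as the baseline measurement". Both 3.1.1 and 3.1.2 presume that a same-day assessment with no recorded time came before the reference event.

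**The concern.** A suspected relapse brings the participant to an unscheduled visit, where the BPDAI is scored and OCS may be raised. If the score and the increase carry the same date, the observation that documents the failure is the one that cannot be carried forward. The previous score, normally from the controlled period, becomes the Week 36 value. That sits badly with a composite strategy meant to register rescue as a bad outcome.

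The endpoints affected are steps 4 and 5 of the alpha-controlled hierarchy (SAP 4.1.1). A miss at step 4 stops testing of steps 5 and 6.

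**Working it through.** **1. Which score qualifies.** The two rules side by side:

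| Score relative to the event | SAP 3.3.3 | Protocol 9.4.2.2 |
|---|---|---|
| Earlier date | eligible | eligible |
| Same date, before the new medication or dose | excluded | eligible |
| Same date, after the new medication or dose | excluded | excluded |
| Later date | excluded | excluded |

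The rules differ only in the second row. SAP Section 6 records a change to this same analysis (removal of the severity covariate) but not this one.

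**2. How old the replacement can be.** Protocol Table 2 spaces visits 14 days apart up to Week 8 and 28 days apart afterwards, with windows of ±3 days. The longest interval between consecutive in-window scheduled visits is:
- up to Week 8: 14 + 3 + 3 = 20 days
- after Week 8: 28 + 3 + 3 = 34 days

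An intervening unscheduled score would shorten this; a missed visit would lengthen it.

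**3. One invented record.** Baseline 60, last visit before relapse 4, relapse visit 34 on the day OCS is raised.
- Rule as written: carries 4, change 4 − 60 = −56.
- Inclusive rule: carries 34, change 34 − 60 = −26.

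**4. Effect on the treatment difference.** For each arm let *r* be the share rescued, *s* the share of those whose score shares the event date, and *d* the relapse score minus the carried score. Moving to the inclusive rule raises that arm's mean by *r* × *s* × *d*. The benralizumab − placebo difference moves by

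*r*B × *s*B × *d*B − *r*P × *s*P × *d*P.

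If *s* and *d* are equal between arms, the size of the shift is *g* × *s* × *d*, where *g* is the gap in rescue shares. The documents supply none of these inputs, so every value below is an assumption, and covariate adjustment is ignored.

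| Endpoint | *g* × *s* × *d* | Shift (points) |
|---|---|---|
| Activity, low | 0.10 × 0.25 × 3 | 0.075 |
| Activity, middle | 0.20 × 0.5 × 10 | 1.0 |
| Activity, high | 0.30 × 1.0 × 17 | 5.1 |
| Activity, wider inputs | 0.40 × 1.0 × 30 | 12 |
| Pruritus, low | 0.10 × 0.25 × 4 | 0.1 |
| Pruritus, middle | 0.20 × 0.5 × 8 | 0.8 |
| Pruritus, high | 0.30 × 1.0 × 12 | 3.6 |

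The activity result runs from under 0.1 to 12 points depending only on what is assumed. The table shows the mechanism and is not an estimate. The shift is zero if no dates coincide, or if rescue rates, same-day shares and score gaps are all equal between arms. Equal rescue rates alone are not enough.

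**5. Direction.** With similar *s* and *d*, more rescue on placebo means the rule as written flatters placebo more and narrows the difference.

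**The case against.** The strongest reply is that the SAP has simply chosen one of two workable conventions. A reader might infer that same-day scores are left undefined. They are not: the wording excludes them, and it can be programmed as it stands. The IGA rules in SAP 3.4.4 use the same cut-off. This stands, so the issue is which convention was chosen.

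A second reply is that medication is recorded by date, dose and frequency (protocol 6.5), without a time of day. A strict cut-off guarantees that no score taken after the new dose is carried; an inclusive one does not. The presumption in SAP 3.1.1 and 3.1.2 is also easier to defend, because protocol 6.1.1 puts visit procedures before study-drug injection, whereas OCS is taken daily at home. This stands in part. For BPDAI-Pruritus the stated visit order supports the presumption when the dose change is decided at that visit. For the clinician-rated activity score no order is stated.

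Third, the frequency is unknown. The protocol also allows the BPDAI to be done as soon as possible after the relapse, and an increase recorded from the next day leaves the relapse score eligible. A reader might infer that relapse scores are dropped as a rule; the documents support this only for coinciding dates.

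Fourth, a reader might infer that the rule favours benralizumab or inflates type I error. The documents do not support that. Step 4 is reached only after steps 1 to 3 succeed in favour of benralizumab, and step 2 already counts rescue and restricted medication as failure. More rescue on benralizumab would also show at step 2 and in the rescue-medication summary of SAP 4.2.3.

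**Conclusion.** The point holds as a narrow, low-priority correction. SAP 3.3.3 and 3.3.4 exclude a same-day relapse score that protocol 9.4.2.2 would keep if it preceded the higher dose or restricted medication. The value substituted normally understates the failure that the composite strategy is meant to capture, and Section 6 does not declare the narrowing.

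Its size cannot be derived from the documents. If rescue is more frequent on placebo, with similar same-day shares and score gaps in both arms, the consequence is conservative: some loss of power at steps 4 and 5, and at step 6 through the gatekeeping. No inflation of type I error is shown. LOCF itself is the prespecified strategy in both documents and is not in question.

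**What to change.** In both event sentences of SAP 3.3.3 and in their baseline follow-ups, replace *prior to the date* with *on or before the date*. Add that an on-site assessment on the event date is taken as preceding the event unless a recorded time shows otherwise. Section 3.3.4 then inherits the rule. Record it in Section 6 before unblinding.

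Use the same convention for the on-site IGA summaries (3.4.4) and for AB-QoL (3.6.2), which borrows the IGA approach. Exempt Peak Pruritus explicitly, because 3.6.1 borrows that approach too. After Visit 2 it is scored at home between 17:00 and 23:59 (protocol Table 3), so a same-day score would normally follow a dose change made at a daytime visit. It is also carried as a weekly mean, which has no single event-day value.

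The cost is SAP wording and programming; no new data are needed, since the relapse-visit BPDAI is already required. The downside is that a same-day score taken after the new dose could be included, mainly for clinician-rated scores such as BPDAI activity, which have no stated order within the visit. Scores dated after the event stay excluded.

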3.4 Secondary efficacy outcome variables

3.4.1 Proportion of participants in sustained complete/partial remission on minimal OCS/off OCS for at least 2 months at Week 36

A supportive responder analysis will be performed where any participants who achieve complete or partial remission while on minimal OCS or off OCS for at least 2 months at Week 36 will be defined as responders.

The same derivation rules and the same intercurrent events described for the primary analysis will be applied.

3.4.2 Cumulative time (weeks) in complete remission off OCS from baseline to Week 36

Cumulative time in complete remission while off OCS will be derived for each participant over the initial 36-week treatment period.

Cumulative time in complete remission while off OCS will be computed summing the days included in all the time intervals between each remission and the following relapse according to the below rules.

If there is no OCS usage from and inclusive of the date when complete remission is assessed until the day before the date of relapse, then cumulative time in complete remission while off OCS will be computed in weeks as:

$$(date\ of\ relapse - date\ of\ complete\ remission) / 7$$

If there is OCS usage on the date of complete remission and the complete remission is confirmed at a later assessment after the OCS usage stop date, then cumulative time in complete remission while off OCS will be computed in weeks as:

$$(date\ of\ relapse - first\ day\ off\ OCS\ after\ remission\ and\ before\ relapse) / 7$$

If the OCS usage stop date is after the last assessment of complete remission then the time will be imputed as equal to zero.

If there is OCS usage after complete remission off OCS that is before or on the day prior to the date of relapse then, the cumulative time in complete remission while off OCS will be computed in weeks as:

$$(last\ day\ off\ OCS\ after\ remission\ and\ before\ OCS\ restart - date\ of\ complete\ remission + 1) / 7$$

For participants who do not have a relapse after a complete remission, the time interval from the complete remission until the date of the BP disease state allocated to Week 36 will be considered for computing the cumulative time in the interval.

For more details about definition of days on or off OCS see Section [3.1.5.1](#).

These times will then be assigned to a set of ordered categories:

- Category Value = 0 for cumulative time = 0 days
- Category Value = 1 for $0 < \text{cumulative time} \leq 56$ days (8 weeks)
- Category Value = 2 for $56 \text{ days (8 weeks)} < \text{cumulative time} \leq 112$ days (16 weeks)
- Category Value = 3 for $112 \text{ days (16 weeks)} < \text{cumulative time} \leq 168$ days (24 weeks)
- Category Value = 4 for cumulative time > 168 days (24 weeks)

Depending on the distribution of the data, categories might be condensed or expanded. Any such decisions will be documented prior to unblinding.

The set of intercurrent events for this estimand consists of participants who receive medications deemed to be intercurrent events as per Section [3.1.5.2](#) and participants who withdraw from the study.

Participants who receive medications deemed to be intercurrent events as per Section [3.1.5.2](#) will be considered with a relapse on the date of start of restricted medications. For restricted medications during the study missing/partial start dates are not allowed.

Participants who withdraw from the study will be considered with a relapse starting after the last available BP disease state clinical assessment.

Note that the list of intercurrent events does not include increases in OCS dose after achieving disease control, and all doses of OCS will be included in the derivation of cumulative time in complete remission while off OCS.

3.4.2.1 Cumulative time (weeks) in complete or partial remission off OCS from baseline to Week 36

Cumulative time (weeks) in complete or partial remission off OCS from baseline to Week 36 will be also computed, as additional endpoint analysed in an exploratory way.

Derivation rules and intercurrent events described in Section [3.4.2](#) for the cumulative time in complete remission while off OCS will be applied.

3.4.3 Proportion of participants off OCS by Week 36

Participants will be defined as responders if they are off OCS by Week 36. Otherwise, participants will be classified as non-responders.

A participant will be considered off OCS at Week 36 if the participant is off OCS prior to the date of the BP disease state allocated to Week 36. Further details on the definition of days off OCS are contained in Section [3.1.5.1](#).

The set of intercurrent events for this estimand consists of participants who receive medications deemed to be intercurrent events as per Section [3.1.5.2](#) and participants who withdraw from the study. The primary estimand will regard these participants as non-responders from the time such events occur up to Week 36.

Participants who withdraw from the study will be considered non-responders starting from the last contact with the participant.

Participants who receive medications deemed to be intercurrent events as per Section [3.1.5.2](#) will be considered non-responders starting from the date of start of restricted medications. For restricted medications during the study missing/partial start dates are not allowed.

3.4.4 IGA score at Week 36 and change from baseline in IGA score at Week 36

An IGA scale uses clinical characteristics to assess overall disease severity at any given time point. This scoring system allows clinicians to rate skin disease activity by general overall impressions. This IGA scale uses key signs of BP with ordinal levels of severity. The IGA is a 5-point categorical scale ranging from 0 (clear) to 4 (severe) with higher scores indicating greater disease activity or damage ([Table 5](#)). The IGA uses clinical characteristics based on the number of lesions, blisters, erosions, erythema and the number of anatomical locations. The IGA scale will be completed at the site by the investigator at the visits specified in the CSP Table 2.

Table 5 IGA Scores and Descriptions

Score	Description
0 – Clear	No skin lesions
1 – Almost Clear	Very few small skin lesions
2 – Mild	Few skin lesions
3 – Moderate	Multiple lesions in > 1 anatomical area OR any large erosive area
4 – Severe	Extensive skin lesions/erosive areas

Note: Examples of skin lesions include blisters, small round erosions, and erythema.

IGA score achieved (clear, almost clear, mild, moderate, severe) will be summarized using descriptive statistics by treatment group at each scheduled visit up to Week 36.

For the summary statistics the following approach will be applied to handle intercurrent events and missing data.

- Participants who receive medications deemed to be intercurrent events as per Section 3.1.5.2 will have their last observed value prior to the date of start of restricted medication carried forward to subsequent visits. If baseline is the last available assessment prior to the date of start of restricted medication, then it will be used to impute the missing data.
- Participants who need to increase their OCS dose as a rescue therapy to treat their BP after having previously achieved disease control will have their last observed value prior to the date of OCS dose increase recorded with start date > date of disease control assessment carried forward to subsequent visits. If baseline is the last available assessment prior to the date of OCS dose increase, then it will be used to impute the missing data.
- For participants who withdraw from the study without having rescue or restricted medications, missing values will remain missing. The same approach will be applied to those participants with missing data for any other reason.

A responder analysis will be performed where participants will be classified as responders if they achieve IGA 0/1 (ie, clear or almost clear) at Week 36. Otherwise, participants will be classified as non-responders.

The same derivation rules and the same intercurrent events as described for the primary analysis will be applied whereby patients with the intercurrent events will be considered as non responders in the analysis.

3.4.5 Proportion of participants who remain relapse-free up to Week 16

The same derivation rules and the same intercurrent events described for the key secondary analysis on the proportion of participants who remain relapse-free up to Week 36 will be applied for the analysis of the proportion of participants who remain relapse-free up to Week 16.

3.4.6 Proportion of participants with any clinical benefit at Week 16

Participants will be defined as responders if they are in partial remission or complete remission at Week 16 as assessed by Investigator. Otherwise, participants will be classified as non-responders.

Responders will be further categorized based on their disease status and OCS data into:

- Partial remission
 - On minimal steroid (less than or equal to 0.1 mg/kg/day of OCS)
 - Off steroid therapy
- Complete remission
 - On minimal steroid (less than or equal to 0.1 mg/kg/day of OCS)
 - Off steroid therapy

3.4.7 Time to disease control, OCS dose at disease control and time to the end of the consolidation phase

As detailed in Section 3.2, Investigators will be asked to make a clinical assessment of the participants to determine their BP disease state.

Disease control is achieved at the time when new lesions cease to form, and established lesions begin to heal, or pruritic symptoms start to abate.

The time (weeks) from randomization to disease control is defined as follows:

$$(date\ of\ first\ assessment\ of\ disease\ control - date\ of\ randomization + 1) / 7$$

Participants who do not reach disease control will be reported as having missing time to disease control.

For the Kaplan Meier analyses, the time from randomization to disease control for participants who do not reach disease control will be censored at the date of the Week 36 assessment for participants who complete the double-blind period. Participants who withdraw from the study

or are lost to follow-up before the Week 36 assessment will be censored at the last visit date after which disease state could not be assessed (ie, at the last non-missing disease state clinical assessment).

OCS dose (mg/kg) at disease control will be calculated for each participant as the dose recorded by the Investigator as per Section 3.1.5.1 on the day before the clinical assessment of disease control.

To compute the dose in mg/kg the baseline weight will be considered.

The handling of partial/missing dose or dates for OCS is detailed in Section 3.1.5.1.

The end of the consolidation phase is defined as the time at which no new lesions have developed for a minimum of 2 weeks and approximately 80% of lesions have healed and pruritic symptoms are minimal, as per Investigator assessment.

The time (weeks) from randomization to end of the consolidation phase is defined as follows:

$(\text{date of end of the consolidation phase} - \text{date of randomization} + 1) / 7$

For the Kaplan Meier analyses, the time from randomization to the end of the consolidation phase for participants who do not reach the end of the consolidation phase will be censored at the date of the Week 36 assessment for participants who complete the double-blind period. Participants who withdraw from the study or are lost to follow-up before the Week 36 assessment will be censored at the last visit date after which disease state could not be assessed (ie, at the last non-missing disease state clinical assessment).

All the data in the double-blind period will be included.

3.4.8 Change from baseline in BPDAI activity score at Week 16

The same derivation rules and the same intercurrent events described for the key secondary analysis on the change from baseline in BPDAI activity score at Week 36 will be applied for the analysis of the change from baseline in BPDAI activity score at Week 16.

3.4.9 Change from baseline in BPDAI-Pruritus score at Week 16

The same derivation rules and the same intercurrent events described for the key secondary analysis on the change from baseline in BPDAI-Pruritus score at Week 36 will be applied for the analysis of the change from baseline in BPDAI-Pruritus score at Week 16.

